#### 4.1.4 *Patient management at the end of treatment*

The trial treatment is stopped after V3.

After the follow-up period (V4, 4 weeks after V3) the Investigator/hepatologists/general practitioner will decide according to each patient, the need to use the lifestyle changes recommendations whenever appropriate and treatment of comorbidities which may play a role in NASH such as, for example, diabetes and hyperlipidaemia.

If the study is positive there will be further trials for which these patients may be eligible.

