- an Analysis of Covariance (**ANCOVA**) using the SAS MIXED procedure with the treatment and the diabetic status as covariates when specified

Or

- a Mixed Model for Repeated Measures (**MMRM**) when specified using the SAS MIXED procedure with:
  - a. The absolute change from baseline of the analysis variable as endpoint (MODEL statement of the MIXED procedure)
  - b. The time, treatment, the diabetic status, the interaction (treatment \* time) and the baseline value as fixed effects (MODEL statement of the MIXED procedure). Time, treatment and diabetic status being considered as categorical variables
  - c. A time repeated measure (REPEATED statement of the MIXED procedure) within each subject (SUBJECT = subject as option of the REPEATED

statement). An unstructured (type=UN) variance covariance matrix being used as option of the REPEATED statement

- d. The Kenward-Roger approximation to estimate denominator degrees of freedom and adjust standard errors (ddfm=kr option in MODEL statement)

In order to explore the validity of the model (and more accurately the assumption regarding independence, normality and constant variance of residuals), the following graphs will be provided: Q-Q plot of the residuals, distribution of residuals with its corresponding normal density estimate and scatterplot of residuals vs. predicted values.

With such models (ANCOVA, MMRM) different treatment effects will be evaluated:

- **Evaluation of treatment effect (Each dose vs. placebo) at week 24:** In order to evaluate each treatment dose versus placebo at week 24 the following contrasts of interest will be used:
  - o 800 mg/day vs. placebo: -1 for Placebo, 1 for 800 mg/day and 0 for 1200 mg/day
  - o 1200 mg/day vs. placebo: -1 for Placebo, 0 for 800 mg/day and 1 for 1200 mg/day.

In order to take into account multiplicity of tests, the ascending Hochberg procedure will be applied (see section 4.1.5).

- **Evaluation of dose effect (800 mg vs. 1200 mg) at week 24:** In order to evaluate the dose of 800 mg/day versus the dose of 1200 mg/day at week 24 the following contrast of interest will be used:
  - o 800 mg/day vs. 1200 mg/day: 0 for Placebo, -1 for 800 mg/day and 1 for 1200 mg/day
- **Time course of the response of each treatment group:** In order to evaluate the time course of the response of each dose (separately) at each time-point the following contrasts of interest will be used for each dose:

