  - o week 4 vs. week 14: -1 for week 4, 1 for week 14, 0 for week 24 and 0 for week 28
  - o week 4 vs. week 24: -1 for week 4, 0 for week 14, 1 for week 24 and 0 for week 28
  - o week 4 vs. week 28: -1 for week 4, 0 for week 14, 0 for week 24 and 1 for week 28
  - o week 14 vs. week 24: 0 for week 4, -1 for week 14, 1 for week 24 and 0 for week 28
  - o week 14 vs. week 28: 0 for week 4, -1 for week 14, 0 for week 24 and 1 for week 28
  - o week 24 vs. week 28: 0 for week 4, 0 for week 14, -1 for week 24 and 1 for week 28

In order to take into account multiplicity of tests, the ascending Hochberg procedure will be applied (see section 4.1.5).

Lowest dose will always be considered as reference for treatment effect calculation. As well as earliest visit will always be considered as reference for time course evaluation.

Comparisons of treatment groups for **qualitative variables** will be done using the FREQ procedure with Cochran–Mantel–Haenszel (CMH) test option, stratified on the diabetic status at Baseline (yes/no). The primary measure of the effect size will be the CMH odds ratio with an adjustment for diabetic status. Because the odds ratio is not easy to interpret when the rate of responders in the placebo group is not very small the odds ratio (OR) will be converted in

Risk Ratio (RR) using the following formula  $RR = (P1/P0) = OR/[(1-P0) + (P0 \times OR)]$ . The same formula will be applied to OR 95% CI lower and upper bounds to obtain RR 95% CI. The log-binomial model will preferentially be used in the absence of convergence or estimability issue for estimating the effect size with RR. The primary handling of heterogeneity of result across strata will be performed through the Breslow-Day test. If the homogeneity hypothesis is rejected, then the estimate of the difference in percentage points between each dose and placebo along with the 95% C.I. will be provided within each stratum, as well as the p-value of the association test between treatment and qualitative variable (Chi-2 test or Fisher's exact test). If the interaction between stratum and treatment (Breslow Day test) is significant it means that the treatment effect has not the same magnitude in diabetic and non-diabetic patients. In the absence of qualitative interaction there will be no further adjustment of the type one error for multiplicity of testing. Smallest dose will always be considered as reference for OR/RR calculation.

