###### Note:

- Data collected at Visit 3 being an early treatment discontinuation, should not be taken into account for Week 24 (i.e. actual V3) data descriptions
- For OCUT analysis where data available at Week 28 (i.e. V4) should be described, all Week 28 (i.e. V4) data that are within 4 weeks  $\pm$  2 weeks compared with Week 24 (i.e. V3) are to be taken into account.  
Data collected at Visit 4 being the visit following an early treatment discontinuation, should not be taken into account for Week 28 (i.e. actual V4) data descriptions
- For all analysis based on biopsy data, data collected at actual V3 should be taken into account as well as data collected at Visit 3 being an early treatment discontinuation.

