#### - Descriptive analysis

Fasting glucose and HbA1c assessed at Screening, Baseline, Week 4, Week 14, Week 24 and Week 28, as well as insulin, C-peptid, fructosamide and HOMA index assessed at Week 0 and Week 24, will be described over time using descriptive statistics by treatment group and diabetic status, in terms of:

- Raw values
- Absolute change from baseline

The 95% CI of the mean will also be provided.

- Status over time (Normal-Normal, Normal-Abnormal, Abnormal-Normal, Abnormal-Abnormal)

The 2 timepoints prior to first intake will have to be analysed: screening and baseline.

One graph will also be provided describing the raw values (with 95% CI) by treatment group over time (including screening values)

The HOMA index will also be described qualitatively over time using descriptive statistics by treatment group and diabetic status (HOMA < 3, ≥ 3).

- Absolute changes in HbA1c value will be described qualitatively over time using descriptive statistics by treatment group and diabetic status:
  - o Decrease of HbA1c (Decrease of 1%, No change (Change within ]-1% ; 1%[]), Increase ≥ 1%).
  - o Decrease of HbA1c (Decrease ≥ 0.5%, No change (Change within ]-0.5% ; 0.5%[]), Increase ≥ 0.5%)
- Evaluation of treatment effect (each dose versus placebo)

For fasting glucose, HbA1c, insulin and HOMA index, in order to evaluate each treatment dose versus placebo at week 24, a MMRM will be performed as detailed in section 4.1.5.

In order to take into account multiplicity of tests, the ascending Hochberg procedure will be applied (see section 4.1.5 for details).

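### The MMRM in SAP 4.1.5 fits one baseline slope across weeks 4, 14, 24 and off-drug week 28, which may cost some week-24 precision on nine laboratory endpoints

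*SAP*

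**What the plan says.** SAP 4.1.5 defines the MMRM as follows.

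- Response: "The absolute change from baseline of the analysis variable as endpoint".
- Fixed effects: "The time, treatment, the diabetic status, the interaction (treatment \* time) and the baseline value as fixed effects". Only treatment is crossed with time. Baseline value and diabetic status are main effects.
- Covariance: "An unstructured (type=UN) variance covariance matrix being used as option of the REPEATED statement", with Kenward-Roger degrees of freedom.

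The time-course contrasts in the same section cover four post-baseline visits and end with "week 24 vs. week 28: 0 for week 4, 0 for week 14, -1 for week 24 and 1 for week 28". Protocol 4.1.4 states "The trial treatment is stopped after V3", and V3 is week 24, so the week-28 value is taken off drug. These endpoints are analysed on observed cases under treatment. The note in SAP 4.1.6.3 nevertheless retains V4 data: "For OCUT analysis where data available at Week 28 (i.e. V4) should be described", values 4 weeks ± 2 weeks from week 24 count.

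The same model supplies the week-24 tests. SAP 5.2.3.8 says that "in order to evaluate each treatment dose versus placebo at week 24, a MMRM will be performed as detailed in section 4.1.5", with Hochberg adjustment over the two doses. SAP 5.2.3.9 and 5.2.3.10 refer to that methodology for liver enzymes and lipids. Protocol 9.7.4 names a mixed model for repeated measures without listing its terms.

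**The concern.** A single baseline coefficient assumes that change from baseline depends on the baseline value in the same way at every visit. That may not be so. Correlation with baseline can weaken over 24 weeks, and a marker that moves on drug may drift back towards its baseline level once the drug is stopped. The fitted slope is then a compromise between visits. The week-24 comparison is adjusted by a slope that does not suit week 24, and part of any chance baseline imbalance remains in the contrast as extra variance.

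At stake is precision on the dose-versus-placebo tests for laboratory endpoints that Protocol 9.1 lists as secondary. The SAP gives no reason for the common slope. The planned residual plots (Q-Q, distribution, residual against predicted) do not examine slope by visit.

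**Working it through.** **Plan's own figure.** The documents size only the binary primary endpoint. The unpooled formula reproduces that figure: (2.2414 + 0.8416)² × (0.10×0.90 + 0.30×0.70) / 0.20² = 9.505 × 7.5 = 71.3, so 72 per group. No sizing, SD or correlation is given for the MMRM endpoints, so the inputs below are assumptions.

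**Which endpoints.** The constraint binds only where there are several post-baseline visits: fasting glucose and HbA1c (SAP 5.2.3.8), ALT, AST and GGT (5.2.3.9), and total cholesterol, HDL-C, LDL-C and triglycerides (5.2.3.10). Insulin and HOMA are assigned to the MMRM but are measured after baseline only at week 24.

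**Formula.** Take SD 1 at baseline and at every visit, and let r_t be the correlation of visit t with baseline.

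- Slope of change on baseline: b_t = r_t − 1.
- Residual variance: s_t² = 1 − r_t².
- S is the residual covariance matrix, with the same residual correlation between every pair of visits.
- The common slope settles at b_c = (1ᵀS⁻¹b) / (1ᵀS⁻¹1).
- The large-sample week-24 contrast variance is (2/n)[s₂₄² + (b₂₄ − b_c)²], against (2/n)s₂₄² with visit-specific slopes.
- Proportional excess = (b₂₄ − b_c)² / s₂₄².

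**Worked cases at residual correlation 0.7.**

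- Pattern 0.92/0.80/0.72/0.70: b₂₄ = −0.28, b_c = −0.037, s₂₄² = 1 − 0.72² = 0.482. Excess = 0.243² / 0.482 ≈ 0.12.
- Rebound 0.60/0.50/0.40/0.80: b₂₄ = −0.60, b_c = −0.182, s₂₄² = 0.84. Excess = 0.418² / 0.84 ≈ 0.21.

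| Assumed r at weeks 4/14/24/28 | Excess, residual correlation 0.3 | Excess, residual correlation 0.7 |
|---|---|---|
| 0.70/0.70/0.70/0.70 | 0% | 0% |
| 0.80/0.72/0.67/0.65 | 0.7% | 1.8% |
| 0.85/0.70/0.60/0.58 | 3.9% | 11.4% |
| 0.92/0.80/0.72/0.70 | 4.5% | 12.3% |
| 0.60/0.50/0.40/0.80 (rebound) | 8.6% | 20.8% |

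In the declining patterns week 4 has the largest weight in the common slope and week 28 adds little. In the rebound pattern week 28 takes 53% to 99% of the weight.

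**Simulation.** Both models were fitted with unstructured covariance: 82 per arm (247/3), complete data, no treatment effect, residual correlation 0.6, 1,500 runs per pattern. Mean model SE, common against visit-specific slopes:

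- equal slopes (all 0.7): 0.1118 v 0.1118;
- 0.8/0.7/0.6/0.6: 0.1279 v 0.1257 (+1.8%);
- rebound: 0.1539 v 0.1433 (+7.4%).

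Across these and one more extreme pattern, the largest bias of the common-slope model was 0.007 and its type I error was 0.043 to 0.052. In the rebound pattern, leaving week 28 out of the common-slope model cut the empirical SE from 0.1543 to 0.1452, against 0.1437 with visit-specific slopes.

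**Drop-out.** In 400 runs with drop-out of roughly 10%, rising with baseline, in one arm and 5% in the others, the week-24 bias in SD units (common v visit-specific) was 0.028 v 0.010, 0.022 v 0.000 and 0.003 v −0.008 for the steepest to the flattest declining pattern. Simulation error was about 0.005 to 0.006. Another run, with 10–13% baseline-dependent drop-out in one arm, gave 0.041 v 0.006.

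**The case against.** A main-effect baseline with unstructured covariance and Kenward-Roger is a valid analysis of a randomised trial. A reader might infer that the SAP adjusts week 24 with a wrong slope and is bound to lose power. The documents do not support that: they give no slope, SD or correlation by visit, and with equal slopes nothing is lost. This stands.

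A reader might also infer that the week-24 difference is biased. With complete data it is not. The drop-out results need drop-out that depends on baseline in one arm only, which no document indicates, and they range from 0.003 to 0.041 SD as the assumptions change. Week-24 values can be missing by design, because SAP 4.1.6.3 excludes early-termination V3 data and sets values more than 3 days after last intake to missing. So bias is possible, but its size is illustrative only.

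The presence of week 28 in the model for the week-24 test is an inference from the time-course contrasts and the V4 note. It is the likely reading, but SAP 5.2.3.8 does not say it outright. If week 28 were left out, the constraint would still bind weeks 4, 14 and 24.

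The stakes are modest. The primary analysis and the tested histology endpoints use CMH, and Protocol 9.7.4 places the glucose and lipid comparisons under exploratory analyses. The protocol synopsis does not control multiplicity across parameters. These points limit the importance of the finding. None of them gives a reason to keep the constraint.

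**Conclusion.** The point holds as an efficiency refinement on nine laboratory endpoints. The common slope gains nothing measurable when slopes are equal and costs precision when they differ.

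Under equal SDs and an exchangeable residual correlation of 0.3 to 0.7, the excess week-24 variance is 0 with equal slopes, about 1% to 12% with declining correlations, and about 9% to 21% with a week-28 rebound. For a test with 80% power at two-sided 0.05, excesses of 12% and 21% leave Φ(2.802/√1.12 − 1.96) ≈ 75% and Φ(2.802/√1.21 − 1.96) ≈ 72%. These ranges are not bounds. With serial residual correlation of 0.8, the rebound pattern gives 53%. Nothing in the documents shows which pattern applies.

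The primary CMH analysis, the ANCOVA endpoints, insulin and HOMA are untouched.

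**What to change.** Before database lock, add baseline value by time to the MODEL statement in SAP 4.1.5(b). Keep the unstructured covariance, Kenward-Roger and all contrasts. The cost is one line of text and 3 degrees of freedom (four slopes in place of one) among 247 randomised patients.

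Two optional points:

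- Diabetic status by time could be added for consistency, but the figures above do not test it. With both interactions and complete data, the week-24 contrast equals a week-24 ANCOVA on baseline value and diabetic status. That is not the ANCOVA written in SAP 4.1.5, which names only treatment and diabetic status.
- State whether week 28 enters the model used for the week-24 test. In the rebound pattern, leaving it out recovers most of the loss.

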## 4.5 Derived variables

### 4.5.1 Baseline data and change from baseline

Baseline data will be considered as the last available non-missing data before or equal to the treatment start.

*Note: For biopsies, multiple reading rules (see section 4.5.4.1.1) should be applied before calculating Baseline values.*

Absolute change from baseline will be calculated as follows:

Value at  $V_i$  – Value at baseline, where  $i$  corresponds to a post-baseline value.

Relative change from baseline (in %) will be calculated as follows:

- if Value at baseline is not equal to 0:  $[(\text{Value at } V_i - \text{Value baseline}) / \text{Value at baseline}] * 100$ , where  $i$  corresponds to a post-baseline value.
- if both values at  $V_i$  and at baseline are equal to 0, then the relative change from baseline will be equal to 0%.

Regarding laboratory parameters that are sensitive to the fasting status (Fasting Glucose, HOMA, insulin, C-peptid, Fructosamine, Triglycerides, Total cholesterol, HDL cholesterol, LDL cholesterol, Free fatty acids (FFA), Apoprotein A1, Apoprotein B, Apoprotein C3, Adiponectin, Leptin, FGF-21):

- if the value at Baseline is a non-fasting value when the value at Screening is a fasting value, then the Baseline data will be the value at Screening
- if both values at Screening and Baseline are non-fasting values, then the Baseline data will be the value at Baseline.

Regarding laboratory parameters, the following status will be defined:

- Normal-Normal, if the baseline is within laboratory ranges and all values over time remain within laboratory ranges
- Normal-Abnormal, if the baseline is within laboratory ranges but at least one value over time is not within laboratory ranges
- Abnormal-Normal, if the baseline is not within laboratory ranges and all values over time are within laboratory ranges
- Abnormal-Abnormal, if the baseline is not within laboratory ranges and at least one value over time is not within laboratory ranges

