#### 4.5.6.3 *Laboratory data*

When result is '<x', value to be considered will be 'x-0.01'

When result is '>x', value to be considered will be 'x+0.01'

If after the following replacement a value become < 0 then value is forced to 0.

Baseline will be defined as the last available value before or the same day as first treatment intake.

Before first treatment intake, the last non-missing value before first intake will be selected.

After first treatment intake, in case of retest for a given parameter, the first non-missing value will be selected.

Regarding laboratory parameters that a sensitive to fasting status (Fasting Glucose, HOMA, insulin, C-peptid, Fructosamine, Triglycerides, Total cholesterol, HDL cholesterol, LDL cholesterol, Free fatty acids (FFA), Apoprotein A1, Apoprotein B, Apoprotein C3, Adiponectin, Leptin, FGF-21):

If the status is 'not fasting' and the value remains within laboratory ranges, then this value will be considered as 'fasting' for the analysis. This is applicable for the baseline value (See section 4.5.1) as well as all values collected over time.

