**Sensitivity analysis**

None

**Analysis by subgroups** (descriptive analysis only)

- By diabetic status (Yes, No) for fasting glucose, insulin, C-peptid, HOMA index, fructosamide and HbA1c
- By HbA1c at baseline ( $\leq 6.5\%$ ,  $>6.5\%$ ) for HbA1c

*5.2.3.9 Liver enzymes*

The following table describes for each parameter the collection time and the type of analyses to be done.

Parameter	Collection time	Main analyses (see section 5.2.3.8 describing the methodology)	Sensitivity analyses	Subgroup analyses
ALT	Screening, Baseline, weeks 4, 14, 24 and 28	Descriptive analysis Treatment effect ( each dose versus placebo ) Time course of the response of each treatment group	None	By diabetic status (Yes, No)
AST	Screening, Baseline, weeks 4, 14, 24 and 28	Descriptive analysis Treatment effect ( each dose versus placebo ) Time course of the response of each treatment group	None	By diabetic status (Yes, No)
GGT	Screening, Baseline, weeks 4, 14, 24 and 28	Descriptive analysis Treatment effect ( each dose versus placebo ) Time course of the response of each treatment group	None	By diabetic status (Yes, No)
Alkaline Phosphatase	Screening, Baseline, weeks 4, 14, 24 and 28	Descriptive analysis	None	By diabetic status (Yes, No)
Total Bilirubin	Screening, Baseline, weeks 4, 14, 24 and 28	Descriptive analysis	None	By diabetic status (Yes, No)

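### The MMRM for nine laboratory variables adjusts for one pre-dose value although a second is scheduled; adding it would be a nearly free and probably small gain in precision

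*SAP*

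**What the plan says.** SAP 4.1.5 models "The absolute change from baseline of the analysis variable as endpoint (MODEL statement of the MIXED procedure". The fixed effects are time, treatment, diabetic status and the treatment-by-time interaction, "and the baseline value as fixed effects (MODEL statement of the MIXED procedure". The covariance is unstructured, with Kenward-Roger degrees of freedom.

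SAP 4.5.1 fixes which value is meant: "Baseline data will be considered as the last available non-missing data before or equal to the treatment start". SAP 4.5.6.3 gives the same rule for laboratory data: "Baseline will be defined as the last available value before or the same day as first treatment intake". That is normally V0. The exception concerns fasting-sensitive variables: if V0 was non-fasting and screening was fasting, "then the Baseline data will be the value at Screening". Even then only one value is used.

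Two pre-dose values are scheduled for nine variables with a dose-placebo test at Week 24:

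- SAP 5.2.3.8: "Fasting glucose and HbA1c assessed at Screening, Baseline, Week 4, Week 14, Week 24 and Week 28".
- SAP 5.2.3.9 for ALT, AST and GGT, and SAP 5.2.3.10 for total cholesterol, HDL-C, LDL-C and triglycerides: "Screening, Baseline, weeks 4, 14, 24 and 28".

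Protocol Table 8 shows the same schedule. SAP 5.2.3.8 also states "The 2 timepoints prior to first intake will have to be analysed: screening and baseline", but under descriptive analysis, where it governs tables and a graph.

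**The concern.** A single laboratory reading mixes the patient's usual level with day-to-day and assay variation. A second reading taken before treatment carries further information on that level. Used as a covariate, it can reduce the unexplained variance at Week 24 and so tighten the dose-placebo contrasts.

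Both readings precede randomised treatment, so using both cannot bias the comparison or inflate the type I error. The plan already collects and tabulates the screening value but lets it into the model only as a substitute for V0. What is at stake is some precision on nine secondary variables. No conclusion on the primary endpoint depends on it.

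**Working it through.** **The plan's own figure.** The documents give no sample size, power, SD or correlation for these nine variables. The only sample size is for the binary primary endpoint (SAP 4.2). With unpooled variance, n = (z₀.₉₈₇₅ + z₀.₈₀)² [p₁(1−p₁) + p₂(1−p₂)] / (p₂−p₁)². This gives 71.3, so 72, for 10% against 30%, and 84.4, so 85, for 15% against 35%. Both match the SAP, and neither uses any quantity discussed here.

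**Inputs.**

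- Screening precedes V0 by 2 to 4 weeks, or 2 to 8 weeks when the biopsy is part of screening (Protocol synopsis, study procedures). It therefore lies 24 + 2 = 26 to 24 + 8 = 32 weeks before Week 24, against 24 weeks for V0.
- Correlations are assumed: r₁ for V0 with Week 24, r₂ for screening with Week 24, and r₁₂ for screening with V0.

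**Formula.** The residual variance at Week 24 is proportional to 1 − r₁² with V0 alone. With both values it is proportional to 1 − R², where R² = (r₁² + r₂² − 2r₁r₂r₁₂)/(1 − r₁₂²). The variance ratio is (1 − R²)/(1 − r₁²). Taking change rather than the raw value as outcome makes no difference, because V0 is in the model.

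**Equal correlation (favourable case).** With r₁ = r₂ = r₁₂ = r the ratio is (1 + 2r)/(1 + r)².

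| r | ratio | variance reduction | SE reduction | equivalent extra patients |
|---|---|---|---|---|
| 0.5 | 2.0/2.25 = 0.889 | 11% | 5.7% | 12.5% |
| 0.6 | 2.2/2.56 = 0.859 | 14% | 7.3% | 16% |
| 0.7 | 2.4/2.89 = 0.830 | 17% | 8.9% | 20% |
| 0.8 | 2.6/3.24 = 0.802 | 20% | 10.4% | 25% |

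A simulation with 3 × 75 patients and 4,000 replicates gave ratios of 0.889, 0.836 and 0.798 at r = 0.5, 0.7 and 0.8.

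**Correlation falling with time.** Suppose the patient's true level has exponentially decaying correlation, c between V0 and Week 24, and a share L of each reading's variance is true level, the rest being visit-level noise. With screening s weeks before V0:

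r₁ = L·c, r₂ = L·c^((24+s)/24), r₁₂ = L·c^(s/24).

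- No noise (L = 1): r₂ = r₁ × r₁₂, so the gain is exactly 0. For example, 0.48 = 0.8 × 0.6 gives a ratio of 1.000 (simulation 1.005).
- Noise of 10 to 20% (L = 0.9 to 0.8), c = 0.5 to 0.8 and s = 2, 4 or 8: the variance falls by about 0.1 to 7%, and the SE by at most about 3.5%. This range holds for the SAP's model form, with one baseline slope common to Weeks 4, 14, 24 and 28.
- Upper end: L = 0.8, c = 0.8, s = 2 gives r₁ = 0.640, r₂ = 0.628, r₁₂ = 0.785. Then R² = 0.451 and the ratio is 0.549/0.590 = 0.930, a 7% reduction.

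**The case against.** The strongest case for leaving the plan alone is that nothing in it is wrong. Baseline-adjusted change with an unstructured covariance and a pre-specified last-pre-dose baseline is a sound analysis. No power target exists for these variables. Protocol 9.7.4 even places the glucose and lipid comparisons under exploratory analyses, although Protocol 9.1 lists them as secondary endpoints. This stands, and it limits the point to an optional refinement.

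Screening is also not a clean replicate of V0. Under Protocol 4.2.3 several lipid-modifying and glucose-lowering drugs need be stopped only by the time of randomisation, so the two readings may reflect different background medication. Entry limits on ALT, HbA1c, glucose and triglycerides narrow the range of screening values. Both points count against the equal-correlation figures. They do not show that the gain is nil. It vanishes only if screening predicts nothing beyond V0, and visit-level noise of any size leaves some gain in the decaying-correlation case.

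A reader might infer three stronger things that the documents do not support:

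- *Every dose-placebo interval would narrow, by 11 to 20% in variance.* That range needs screening to predict Week 24 as well as V0 does. If it adds nothing, the extra covariate can cost a trace of precision.
- *Both values exist for every patient.* Protocol Table 1 and Protocol 9.1 tie HbA1c to patients with type 2 diabetes, although Protocol Table 8 and SAP 5.2.3.8 do not. Only fasting glucose and lipid results are analysed, so some screening values may be unusable.
- *The outcome could simply be change from V0.* That would conflict with SAP 4.5.1, where screening can itself become the baseline.

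The point also does not reach insulin, HOMA index, apoA1 or adiponectin, which have one scheduled pre-dose value.

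**Conclusion.** The point holds as a missed efficiency of the lowest severity. The model uses one pre-dose value where two are scheduled for nine variables, and no section combines them. The expected reduction in residual variance at Week 24 is about 0 to 7% if correlation declines with time. The 11 to 20% range is an upper case that requires equal correlation of 0.5 to 0.8 across all visits. Both ranges rest on assumed correlations.

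The planned analysis remains valid without the change, and the primary CMH analysis and the 72 (rounded to 75) per group are untouched. The case for acting is that the value is already scheduled and its use cannot bias the comparison. It does not rest on a large expected gain.

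**What to change.** Amend SAP 4.1.5 before database lock and unblinding. For ALT, AST, GGT, fasting glucose, HbA1c, total cholesterol, HDL-C, LDL-C and triglycerides:

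- Add the V-1 screening value as a second pre-dose covariate. Keep the outcome as change from baseline as defined in SAP 4.5.1.
- Use the V-1 value, not the retest, when a retest exists. Protocol 5.3.2 makes a retest mandatory when screening exceeds 4 weeks, so some patients have three pre-dose values.
- Apply the rule in SAP 4.5.6.3 that treats in-range non-fasting results as fasting before deciding whether a screening value is usable.
- Set the second covariate to its overall mean, taken across all arms, where the screening value is missing, is still non-fasting for a fasting-only analysis, or already serves as the baseline under SAP 4.5.1.

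The cost is one model term, one derived variable for each of the nine parameters, and the corresponding dataset quality control under SAP 4.1.3. No new data, visits or samples are needed.
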